4.1.2 Exclusion Criteria

Patients who meet any of the following criteria will be excluded from study entry:

GA Characteristics Exclusion Criteria

- GA in either eye due to causes other than AMD (monogenetic macular dystrophies [e.g., Stargardt disease, cone rod dystrophy] or toxic maculopathies [e.g., chloroquine/hydroxychloroquine maculopathy])

Ocular Exclusion Criteria: Study Eye

- History of vitrectomy surgery, submacular surgery, or any surgical intervention for AMD
- Previous laser photocoagulation for CNV, diabetic macular edema, retinal vein occlusion, and proliferative diabetic retinopathy
- Prior treatment with Visudyne[®], external-beam radiation therapy (for intraocular conditions), or transpupillary thermotherapy
- History of prophylactic subthreshold laser treatment for AMD
- Previous intravitreal drug delivery (e.g., intravitreal corticosteroid injection, anti-angiogenic drugs, anti-complement agents, or device implantation). A single intraoperative administration of a corticosteroid during cataract surgery for cystoid macular edema prophylaxis at least 3 months prior to screening is permitted.

Ocular Exclusion Criteria: Non-Study Eye

- Non-functioning non-study eye defined as either:
 - BCVA of hand motion or worse
 - OR
 - No physical presence of non-study eye (i.e., monocular)

Ocular Exclusion Criteria: Both Eyes

- Previous participation in interventional clinical trials for geographic atrophy or dry AMD (except of vitamins and minerals) irrespective of the route of administration (ocular or systemic)
- Previous treatment with eculizumab, lampalizumab, fenretidine or any other drugs for geographic atrophy or dry AMD treatment

Ocular Exclusion Criteria: Concurrent Ocular Conditions

- RPE tear that involves the macula in either eye
- Any concurrent ocular or intraocular condition in the study eye (e.g., cataract or diabetic retinopathy) that, in the opinion of the investigator, could do either of the following:
 - Require medical or surgical intervention during the study period to prevent or treat vision loss that might result from that condition
 - If allowed to progress untreated, could likely contribute to loss of at least two Snellen equivalent lines of BCVA during the study period
- Active uveitis and/or vitritis (grade trace or above) in either eye
- History of idiopathic or autoimmune-associated uveitis in either eye
- Active, infectious conjunctivitis, keratitis, scleritis, or endophthalmitis in either eye
- Current vitreous hemorrhage in the study eye
- History of retinal detachment or macular hole (Stage 3 or 4) in the study eye
- Aphakia or absence of the posterior capsule in the study eye
- Previous violation of the posterior capsule in the study eye unless it occurred as a result of yttrium aluminum garnet (YAG) laser posterior capsulotomy in association with prior posterior chamber intraocular lens implantation
- Spherical equivalent of the refractive error in the study eye demonstrating >8 diopters of myopia
- For patients who have undergone prior refractive or cataract surgery in the study eye, the preoperative refractive error in the study eye should not have exceeded 8 diopters of myopia.
- Intraocular surgery (including cataract surgery) in the study eye within 3 months preceding Day 1
- Uncontrolled glaucoma in the study eye (defined as intraocular pressure [IOP] ≥ 30 mm Hg despite treatment with anti-glaucoma medication)
- History of glaucoma-filtering surgery in the study eye
- History of corneal transplant in the study eye
- Proliferative diabetic retinopathy in either eye
- Prior or active CNV in either eye
- Central serous retinopathy in either eye

Lampalizumab—F. Hoffmann-La Roche Ltd
51/Protocol GX29176, Version 6

- History of recurrent infectious or inflammatory ocular disease *in either eye*

Concurrent Systemic Conditions Exclusion Criteria

- Uncontrolled blood pressure (defined as systolic >180 mm Hg and/or diastolic >110 mm Hg while patient is sitting)

If a patient's initial measurement exceeds these values, a second reading may be taken 30 or more minutes later. If the patient's blood pressure must be controlled by anti-hypertensive medication, the patient can become eligible if medication is taken continuously for at least 30 days prior to Day 1.

- History of other diseases, metabolic dysfunction, physical examination finding, or clinical laboratory finding that gives reasonable suspicion of a disease or condition that contraindicates the use of lampalizumab or that might affect interpretation of the results of the study or that renders the patient at high risk of treatment complications
- Treatment for active systemic *or localized* infection

The ongoing prophylactic use of antimicrobial therapy should be discussed with the Medical Monitor.

- Predisposition or history of increased risk of infection (i.e., history of splenectomy or chronic immunosuppression)
- Active cancer within past 12 months except for appropriately treated carcinoma in situ of the cervix, non-melanoma skin carcinoma and prostate cancer with a Gleason score of <6 and a stable prostate-specific antigen (PSA) for > 12 months.
- History of allergy to fluorescein that is not amenable to treatment
- History of a severe allergic reaction or anaphylactic reaction to a biologic agent or known hypersensitivity to any component of the lampalizumab injection
- Inability to comply with study or follow-up procedures
- Inability to obtain CFP, FAF, and FA of sufficient quality to be analyzed and graded by the central reading center
- Previous participation in any studies of investigational drugs within 3 months (except as listed in the above Section 'Ocular Exclusion Criteria: Both Eyes') preceding Day 1 (excluding vitamins and minerals)
- Requirement for continuous use of any medications/treatments indicated in the "Prohibited Therapy" section of the protocol (see Section 4.4.2)
- Women who are pregnant or lactating or intending to become pregnant during the study

Women of childbearing potential must have a negative serum pregnancy test result within 28 days prior to initiation of study treatment.

4.1.3 Microperimetry Criteria at Selected Sites Only

Inclusion Criteria

- Patients must meet all other eligibility criteria for study entry.

- Microperimetry screening test criteria for eligibility:
 - Must be able to detect fixation target.
 - Total elapsed time to complete the 10-2 68 point exam is ≤ 30 minutes in duration.
 - Reliability Test ratio $\leq 20\%$ (false positive rate).
 - Ability and willingness to undertake MP assessment as determined by investigator.

Exclusion Criteria

- Any exclusion criteria listed for the study entry
- Investigator determines that patient is unable to perform the test reliably (e.g. Difficulty sitting still against the supporting chinrest for > 10 minutes; Unable to physically operate the clicker or joystick; Unable to follow the instructions for the test [i.e. cognitive impairment])

Note: disqualification from the microperimetry assessment doesn't exclude a patient from the trial participation if she/he qualifies as per the rest of the study entry criteria.

4.2 METHOD OF TREATMENT ASSIGNMENT AND MASKING

4.2.1 Treatment Assignment

After written informed consent has been obtained, all patients will receive a screening number assigned through the Interactive Voice and Web Response Systems (IxRS). A patient must satisfy all eligibility criteria (see Sections 4.1.1 and 4.1.2) at both the screening and the Day 1 visit (first study treatment) prior to randomization. As part of the screening process, the central reading center (masked to patient treatment assignment) will evaluate FAF images, CFP, and FA to provide an objective, masked assessment of patient eligibility. After all patient eligibility requirements are confirmed, site personnel will contact the IxRS on Day 1 visit for assignment of a patient identification number (a separate number from the screening number). Patients will be randomized in a 2:1:2:1 ratio to one of the study treatment arms (lampalizumab Q4W, sham Q4W, lampalizumab Q6W, or sham Q6W). The study treatment kit number will be also assigned by IxRS at that time. Patients will be randomized on the same day the study treatment is to be initiated (Day 1 visit).

Randomization will be stratified by biomarker status (positive vs. negative, as determined by the investigational cobas[®] CFI Profile assay), baseline BCVA ETDRS chart Snellen equivalent (20/50 or better vs. worse than 20/50), sex (woman vs. man), and microperimetry eligibility (yes vs. no). A permuted-block randomization method will be used to obtain an approximately 2:1 ratio between lampalizumab and sham arms for each dosing frequency within each stratum.

Once the study randomizes the allotted number of CFI profile biomarker-negative or CFI profile biomarker-positive patients (see [Figure 2](#)), the additional screened patients who would have been randomized in the already-filled biomarker arms will be screen-failed.

Patients and all study site personnel will be masked for CFI profile biomarker status until study completion. Sponsor study team members who have direct contact with study sites will be masked to CFI profile biomarker status, but team members who do not interact with study sites may review individual patient CFI profile biomarker status.

Details of the randomization procedure will be described in the Statistical Analysis Plan (SAP).

4.2.2 Masking

This is a double-masked study. There must be a minimum of two investigators per site to fulfill the masking requirements of this study. Study visits must be scheduled when both investigators are present. At least one investigator will be designated as the evaluating physician who will be masked to patients' treatment assignment and will evaluate all ocular assessments. At least one other investigator (and designated, unmasked assistant, as needed) will be designated as the treating (injecting) physician who will be unmasked to patients' treatment assignment and will administer injections (lampalizumab or sham). *The Principal Investigator must be masked to patients' treatment assignment. All roles for each study staff member should be clearly documented on the Site Delegation Log. The Delegation Log should be signed by the Principal Investigator.*

Once the designated *masked vs. unmasked* roles are delineated and the site study staff have started to perform them, the roles *cannot* be switched or reversed at any time during the conduct of the study. In case a site is *experiencing* unexpected extreme situations, the Medical Monitor's permission might be granted to switch the study staff member from the masked role to the unmasked role, but not the other way around. In the event an alternate study staff member needs to be added or substituted, that alternate study staff member may assume only one role for the duration of the study.

Starting at the patient's Day 1 visit, the treating physician(s) (performing the lampalizumab or sham injections), *post-treatment finger counting, and optional aqueous humor sample collection*) *must continue their role as treating physician only, cannot* be involved in any other aspect of the study, and must not divulge treatment assignment to anyone.

Patients, study site personnel (with the exception of the treating physician[s], assistant[s], and pharmacist if any), the designated evaluating physician(s), central reading center personnel, and the Sponsor and its agents (with the exception of drug accountability monitors) will be masked to treatment assignment.

The VA examiner (performing the refraction, BCVA examinations, and reading speed assessment) will be masked to patient treatment assignment and the treated study eye and will only perform refraction, BCVA, BCVA under low luminance conditions, and reading speed assessments. The BCVA examiner will have no access to the VA scores of a patient's previous visits and may have access only to patient's refraction data from previous visits. The VA examiner is not allowed to perform any other tasks involving direct patient care.

Every effort must be made to limit the number of unmasked study personnel to ensure the integrity of this masked study. There must be no more than five unmasked personnel at an investigative site at one time. In special circumstances more than five unmasked personnel may be permitted after consultation with the medical monitor.

Documented procedures will be put in place to avoid inadvertently unmasking study team members. Only the IxRS provider and the external iDCC responsible for verifying a patient's randomization and study treatment kit assignment, who are not otherwise involved in the study, will have access to the unmasking code.

For the duration of the study, the patient treatment assignment will not be unmasked unless required for patient safety.

All study visit assessments, except those at screening, should be performed by masked site personnel only. Starting at a patient Day 1 visit, the unmasked treating physician will only perform the study treatment and the 15 minutes post-treatment vision testing (finger counting and, if applicable, hand movement and/or light perception). The injecting physician will also perform a Lucentis injection if it was prescribed for either eye.

Study assessments include PK sample collection in all patients (Section 4.5.9.3). While PK samples must be collected from patients assigned to the sham arm to maintain the masking of treatment assignment, PK assay results for these patients are generally not needed for the safe conduct or proper interpretation of this study. Sponsor personnel responsible for performing PK assays will be unmasked to patients' treatment assignments to identify appropriate PK samples to be analyzed. Samples from patients assigned to the sham arm will not be analyzed except by request (i.e., to evaluate a possible error in dosing).

4.2.3 Unmasking

If unmasking is necessary for patient management (e.g., in the case of a serious adverse event for which patient management might be affected by knowledge of treatment assignment), the investigator will be able to break the treatment code by contacting the IxRS. Treatment codes should not be broken except in emergency situations. If the investigator wishes to know the identity of the study treatment for any other reason, he or she should contact the Medical Monitor directly. The investigator

should document and provide an explanation for any premature unmasking (e.g., accidental unmasking or unmasking due to serious adverse events).

For regulatory reporting purposes and if required by local health authorities, the Sponsor will break the treatment code for all serious, unexpected suspected adverse reactions that are considered by the investigator or Sponsor to be related to study drug.

4.3 STUDY TREATMENT

4.3.1 Formulation, Packaging, and Handling

4.3.1.1 Lampalizumab Formulation

Lampalizumab Drug Product is provided as a sterile, white to off-white, lyophilized powder in a 6-cc USP/European Pharmacopoeia Type 1 glass vial and is intended for intravitreal administration. For the Phase III clinical studies, each glass vial contains a nominal 40 mg of lampalizumab. After reconstitution with Sterile Water for Injection, the drug product is formulated as 100 mg/mL lampalizumab in 40 mM L-histidine hydrochloride, 28 mM sodium chloride, 160 mM sucrose, 0.04% (w/v) polysorbate 20, pH 5.3.

Storage

Upon receipt of lampalizumab, vials should be refrigerated at 2°C–8°C (36°F–46°F) until use. Lampalizumab vials should not be used beyond the expiration date provided by the manufacturer. No preservative is used in lampalizumab drug product; therefore, the vial is intended for single use only. Vial contents should not be frozen or shaken and should be protected from direct sunlight. Within 2 hours following dose preparation (reconstitution), lampalizumab should be administered; the prepared dose may be maintained at room temperature prior to administration.

For further details, see the Lampalizumab Investigator's Brochure and/or Pharmacy Binder.

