The evaluation of the prognostic value of the CFI profile biomarker will be based on the biomarker status at baseline and the primary clinical outcome of change in the GA area from baseline as measured by FAF.

Exploratory Outcome Measures

The exploratory outcome measures for this study are as follows:

- Monocular reading speed as assessed by MNRead charts or Radner Reading Charts over time
- Monocular critical print size as assessed by MNRead charts or Radner Reading Charts over time
- Monocular reading acuity as assessed by MNRead charts or Radner Reading Charts over time
- Binocular reading acuity as assessed by MNRead charts or Radner Reading Charts over time
- Total lampalizumab and factor D levels in aqueous humor as assessed by ELISA
- To evaluate the potential association of genetic variants in CFI and complement-pathway genes with disease characteristics and response to administration of lampalizumab
- To evaluate the relationship of genetic variants in CFI and complement-pathway genes to levels in the blood of mRNA and proteins of CFI and complement-pathway genes

Exploratory Substudies

At selected sites, the Sponsor may propose exploratory substudies associated with the Study GX29176 protocol. Each substudy will be documented in a separate substudy protocol and associated ICF(s).

Investigational Medicinal Products

Lampalizumab

Lampalizumab Drug Product is provided as a sterile, white to off-white, lyophilized powder in a 6-cc USP/European Pharmacopoeia Type 1 glass vial and is intended for intravitreal administration. For the Phase III clinical studies, each glass vial contains a nominal 40 mg of lampalizumab. After reconstitution with Sterile Water for Injection, the Drug Product is formulated as 100 mg/mL lampalizumab in 40 mM L-histidine hydrochloride, 28 mM sodium chloride, 160 mM sucrose, 0.04% (w/v) polysorbate 20, pH 5.3.

Lampalizumab intravitreal injections

A 10-mg dose of lampalizumab will be used in this study and will be administered to patients randomized to lampalizumab treatment arms intravitreally Q4W or Q6W during the 2-year treatment period.

Comparator

Sham vials will be identical to vials of lampalizumab, but the sham vials will be empty.

A sham injection is a procedure that mimics an intravitreal injection of lampalizumab, except that the blunt end of an empty syringe is pressed against an anesthetized eye instead of a needle attached to a lampalizumab-filled syringe.

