4.3.2 Dosage, Administration, and Compliance

4.3.2.1 Lampalizumab and Sham

Dosage

Study treatment should not occur earlier than 22 days after the previous treatment.

Guidelines for treatment interruption or discontinuation are provided in Section [4.6.2](#) and Section [4.4.3](#).

Any overdose or incorrect administration of study drug should be noted on the Study Drug Administration electronic Case Report Form (eCRF). Adverse events

Lampalizumab—F. Hoffmann-La Roche Ltd
56/Protocol GX29176, Version 6

associated with an overdose or incorrect administration of study drug should be recorded on the Adverse Event eCRF.

Lampalizumab Intravitreal Injections

A 10-mg dose of lampalizumab will be used in this study and will be administered intravitreally to patients randomized to the lampalizumab Q4W or Q6W treatment arms during the 2-year treatment period (see [Appendix 1](#) for the study flowcharts).

Sham Injections

Patients randomized to the control arms will receive sham injections Q4W or Q6W during the 2-year treatment period and will undergo the same assessments as the lampalizumab treatment arm (see [Appendix 1](#) for the study flowcharts).

Sham injection is a procedure that mimics an intravitreal injection of lampalizumab, except that the blunt end of an empty syringe is pressed against an anesthetized eye instead of a needle attached to a lampalizumab-filled syringe.

Administration

See [Appendix 4](#) for the pre-injection procedures of both treatments (lampalizumab and sham) for all patients, [Appendix 5](#) for the injection procedures of the study drug, [Appendix 6](#) for the injection procedures of the sham treatment procedure, and [Appendix 7](#) for the post-injection procedures for all treated patients.

Compliance

This study will be conducted in accordance with the U.S. Food and Drug Administration (FDA) regulations; the International Conference on Harmonisation (ICH) E6 Guideline for Good Clinical Practice (GCP); and applicable local, state, and federal laws, as well as other applicable country laws.

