Appendix 5 Preparation and Administration of Lampalizumab Injection

The drug must be reconstituted using a sterile field while personnel (the unmasked technician or treating physician) are wearing a surgical face mask. Within 2 hours following dose preparation (reconstitution), lampalizumab should be administered; the prepared dose may be maintained at room temperature prior to administration.

Reconstitute for the 10-mg lampalizumab dose as follows:

1. Remove the plastic flip-off seal from one vial of lampalizumab lyophilized powder (6-cc vial), and swab the top of the vial with an alcohol swab.
2. Remove the plastic flip-off seal from **one vial of Sterile Water for Injection (SWFI)** (10-cc vial), and swab the top of the vial with an alcohol swab.
3. Using a 1 cc tuberculin (or equivalent) syringe *with an 18 or 19-gauge needle*, withdraw *enough volume* of SWFI (10-cc vial), *to deliver 0.50 mL of SWFI*, expel any air bubbles, insert the *needle* into the lampalizumab vial, and add.
4. Swirl the lampalizumab vial gently until the lyophilized powder dissolves; **do not shake or vortex the vial vigorously**. Let stand for approximately 5 minutes until bubbles dissolve.

Filter the lampalizumab as follows:

1. Withdraw 0.2 mL of lampalizumab dose solution through *an 18 or 19-gauge, 5- μ m filter needle attached to a new 1-cc tuberculin (or equivalent) syringe*.
2. After withdrawing lampalizumab in through the filter; **remove filter needle; replace it with a 30-gauge, 0.5-inch needle** (*without safety needle device attached*); and expel excess lampalizumab *and air bubbles* so that the syringe contains 0.1 mL of lampalizumab solution for dosing.

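### Does a vial of nominally 40 mg, reconstituted with 0.50 mL of water, contradict the stated 100 mg/mL and 10-mg dose?

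*Protocol*

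**What the plan says.** Protocol Section 4.3.1.1 states that "each glass vial contains a nominal 40 mg of lampalizumab" and that, once reconstituted, "the drug product is formulated as 100 mg/mL lampalizumab". The synopsis, under Investigational Medicinal Products, gives the same vial content and the same concentration. Section 4.3.2.1 sets the dose: "A 10-mg dose of lampalizumab will be used in this study and will be administered intravitreally to patients" in the Q4W and Q6W active arms.

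Appendix 5 gives the preparation under the lead-in "Reconstitute for the 10-mg lampalizumab dose as follows". It uses one vial of powder, with enough Sterile Water for Injection drawn up "to deliver 0.50 mL of SWFI". Then 0.2 mL is withdrawn through a filter needle and the excess expelled "so that the syringe contains 0.1 mL of lampalizumab solution for dosing". Table 1 of the same appendix repeats the single vial and the 0.50 mL.

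Neither the protocol nor the SAP defines the word nominal, states an overfill, or gives the final volume after the powder dissolves. Section 4.3.1.1 refers to the Investigator's Brochure and/or Pharmacy Binder for further detail, and Appendix 4 says the Pharmacy Binder also describes reconstitution.

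**The concern.** Anyone who checks the preparation from the vial content forward divides 40 mg by 0.50 mL and gets 80 mg/mL, not 100 mg/mL. The 0.1 mL kept in the syringe would then hold 8 mg, not 10 mg.

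The obvious ways out of this do not work from the printed text:

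- Appendix 5 specifies the volume delivered into the vial, so syringe or needle hold-up does not explain the gap.
- Only one vial is used, so a second cannot make up the difference.
- Dissolved solids that take up space would lower the concentration further.

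If the literal reading were right, the milligram figure that names both active arms would be overstated by the factor 10 / 8.0 = 1.25 or more. Any pharmacokinetic parameter that takes the dose as an input would carry the same error. A dose label that cannot be traced through the protocol's own numbers deserves a check.

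**Working it through.** **Inputs.** Vial content is a nominal 40 mg and stated concentration is 100 mg/mL (synopsis; Section 4.3.1.1). One vial, 0.50 mL of diluent delivered, 0.2 mL withdrawn and 0.1 mL retained (Appendix 5, steps and Table 1). Stated dose is 10 mg (Section 4.3.2.1).

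**The protocol's own dose.** Dose = concentration x injected volume = 100 mg/mL x 0.1 mL = 10 mg. This reproduces the stated dose exactly.

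**Literal reading: 40 mg is the total fill.** Concentration = content / final volume.

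- If the final volume equals the diluent volume, 40 / 0.50 = 80 mg/mL, and 80 x 0.1 = 8.0 mg, which is 1 - 8.0/10 = 20% below 10 mg.
- If the solids add volume, the figure falls. The documents give no final volume. Over an assumed range of 0.525 to 0.60 mL, the concentration is 40/0.525 = 76.2 down to 40/0.60 = 66.7 mg/mL, or 7.6 down to 6.7 mg in 0.1 mL.
- So 80 mg/mL and 8.0 mg are maxima under this reading, provided that dissolving the powder does not shrink the volume below 0.50 mL.

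**What total fill would give 100 mg/mL?** Fill = 100 mg/mL x final volume.

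| Final volume (mL) | Fill needed (mg) | Excess over 40 mg |
|---|---|---|
| 0.50 | 50.0 | 25% |
| 0.525 (assumed) | 52.5 | 31% |
| 0.60 (assumed) | 60.0 | 50% |

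A fill of at least 50 mg is therefore necessary if the final volume is at least 0.50 mL, but it is not sufficient. The fill has to match the final volume: 50 mg in 0.60 mL would give only 83.3 mg/mL, and 60 mg in exactly 0.50 mL would give 120 mg/mL.

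**Deliverable-content reading.** A volume of 40 mg / 100 mg/mL = 0.40 mL corresponds to the printed content. That is 0.40/0.50 = 80% of the diluent volume, so some solution would stay behind in the vial. On this reading nominal content, concentration, diluent volume, injected volume and dose are all consistent. The 0.2 mL that Appendix 5 draws up is well within 0.40 mL.

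**Where the 40 mg is used.** It enters no preparation step. Sites add 0.50 mL, draw 0.2 mL and keep 0.1 mL whatever the label content is.

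**Where milligrams enter the analysis.** The primary and secondary efficacy comparisons are by randomised arm and use no milligram figure. Serum concentrations are summarised descriptively (Protocol Section 6.6; SAP Section 4.6). Only noncompartmental or population pharmacokinetic work could use the dose, and SAP Section 4.6 makes both optional. Both active arms use the same preparation, so a common dose factor cancels between Q4W and Q6W.

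**The case for a change.** The strongest case for acting is that the protocol should stand on its own for something as basic as the dose. The vial content and concentration are printed twice, and the diluent volume twice. All are current text, and they cannot be brought together without a fact that neither document supplies. The protocol defines overdose relative to the dose under study (Section 5.3.5.11) and lists an incorrect dose among medication errors (Section 5.2.3), so the milligram figure has some operational role. The remedy would be cheap: one look at a manufacturing or pharmacy record and one sentence.

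The arithmetic in that case stands, and so does the observation that the term is undefined. The step from there to a defect in the plan does not. The qualifier nominal is printed both times the 40 mg appears, and the deliverable-content reading removes the conflict completely. The protocol names the documents that hold product detail, so the absence of an overfill statement from the protocol and SAP does not show that it is missing from the trial. Staff who judge a dosing error work from kit, vial and volume, all of which Appendix 5 specifies without ambiguity. A clarifying sentence would help a reader who tries the division, but it would alter no injection, no dataset and no planned result.

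**Conclusion.** No change to the plan follows. This is a product detail that the protocol leaves to its supporting documents.

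Read literally as total fill, 40 mg in 0.50 mL gives at most 80 mg/mL and at most 8.0 mg in 0.1 mL, and this does not match the stated 100 mg/mL and 10 mg. Read as deliverable content with an overfill equal to 100 mg/mL times the final volume, less 40 mg, there is no mismatch. From the documents alone, one cannot tell which reading applies. The fill and the reconstituted volume are matters for the sponsor's product record, from which the synopsis, Section 4.3.1.1 and Appendix 5 can be reconciled. No view is taken here on which figure is right.

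For the statistics the size of the issue is nil: the comparison with sham, the Q4W-to-Q6W comparison and the descriptive serum summaries are the same under either reading. An optional dose-based pharmacokinetic parameter would be affected only under the literal reading, and the analyst would take the confirmed dose from the product record in any case. The conclusion assumes that sites prepare by volume as Appendix 5 directs and that both active arms draw on the same vial presentation, as the protocol describes.
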